8.2 Symptom Score Assessment

After signing the informed consent, patients will fill out the Brief Fatigue Inventory (BFI) (Appendix E) and the MD Anderson Symptom Inventory (MDSI) (Appendix F). The patients will fill out the BFI and MDSI forms at Day 1 and every visit to MDACC. These time points were chosen based on our symptom control study of patents with CLL (protocol 2013-0044).

8.3 Disease Response Assessment

Assessment of clinical response will be conducted in accordance with our standard of care (physical examination, CBC, a bone marrow aspiration, and a whole body CT scan to be done at screening and 6 ± 2 months into treatment).

The IWCLL response criteria (Hallek et al., 2008) (Table 8) will be used to assess disease response. A bone marrow aspiration, a whole body CT scan is to be done at screening and 6 ± 2 months into treatment to further assess response. If a 20% reduction in tumor burden is observed at 6 ± 2 months, Treatment will be continued.

Table 8. Response definition after treatment for patients with CLL/SLL, using the parameters of Tables 1 and 3

Parameter	CR*	PR*	PD*
Group A			
Lymphadenopathy [‡]	None > 1.5 cm	Decrease \geq 50%	Increase \geq 50%
Hepatomegaly	None	Decrease \geq 50%	Increase \geq 50%
Splenomegaly	None	Decrease \geq 50%	Increase \geq 50%
Blood lymphocytes	< 4000/ μ L	Decrease \geq 50% from baseline	Increase \geq 50% over baseline
Marrow [‡]	Normocellular, < 30% lymphocytes, no B-lymphoid nodules. Hypocellular marrow defines CRi (5.1.6).	50% reduction in marrow infiltrate, or B-lymphoid nodules	
Group B			
Platelet count	> 100 000/ μ L	> 100 000/ μ L or increase \geq 50% over baseline	Decrease of \geq 50% from baseline secondary to CLL/SLL
Hemoglobin	> 11.0 g/dL	> 11 g/dL or increase \geq 50% over baseline	Decrease of > 2 g/dL from baseline secondary to CLL/SLL
Neutrophils [‡]	> 1500/ μ L	> 1500/ μ L or > 50% improvement over baseline	

Group A criteria define the tumor load, group B criteria define the function of the hematopoietic system (or marrow).

[‡]* CR (complete remission): all of the criteria have to be met, and patients have to lack disease-related constitutional symptoms; PR (partial remission): at least two of the criteria of group A plus one of the criteria of group B have to be met; SD is absence of progressive disease (PD) and failure to achieve at least a PR; PD: at least one of the above criteria of group A or group B has to be met.

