2.1.1 Effect of Ruxolitinib in patients with CLL/SLL

Because no standard therapeutic intervention is available to control CLL/SLL patients' symptoms and because stimulation of the BCR activates the JAK/STAT3 pathway, known to induce the production of inflammatory cytokines (Rozovski et al., 2014), we conducted a clinical trial (protocol 2013-0044) to assess the effect of ruxolitinib on symptoms in CLL/SLL patients. After the enrollment of 40 patients onto this study we found that: **1.)** Ruxolitinib is well tolerated in patients with CLL/SLL. Very few patients had to be removed from the study because of adverse events. **2.)** The vast majority of the patients (78 %) responded to therapy, their symptoms improved, often dramatically, and the clinical improvement in the patients correlated with a significant reduction in plasma inflammatory cytokine levels. **3.)** In several patients, the number of peripheral blood lymphocyte counts increased and then decreased to or below baseline level, as observed in CLL/SLL patients treated with the Bruton tyrosine kinase (BTK) inhibitor Ibrutinib, suggesting that, like Ibrutinib, ruxolitinib induces mobilization and then apoptosis of CLL/SLL cells. Therefore we intend to explore whether ruxolitinib would reduce disease burden in patients with high-risk CLL/SLL.

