2.1.2 Previously untreated patients with high-risk CLL/SLL

[figure not shown]
The clinical course of patients with CLL/SLL is diverse; some patients have indolent disease, never needing treatment, whereas others have aggressive disease requiring early intervention. We currently use clinical criteria to initiate therapy. However several investigators suggested that early intervention in patients with high-risk disease might be beneficial. To determine which patients are at high risk of disease progression, a multivariable analysis was performed to identify prognostic factors independently associated with time to first treatment for patients with CLL (Wierda et al., 2011). This multivariable model was used to develop a nomogram—a weighted tool to calculate 2- and 4-year probability of treatment and estimate median time to first treatment.

The factors independently associated with shorter time to first treatment included: **a.)** three involved lymph node sites, **b.)** increased size of cervical lymph nodes, **c.)** presence of 17p deletion or 11q deletion assessed by fluorescence in situ hybridization (FISH), increased serum lactate dehydrogenase (LDH), and unmutated IgHV (Wierda et al., 2011).

Given that ruxolitinib is well tolerated and efficiently alleviates the symptoms of patients with CLL/SLL and given that, similar to ibrutinib, treatment with ruxolitinib increased and then reduced the number of circulating lymphocytes, we sought to investigate the clinical benefits of ruxolitinib in patients with previously untreated high-risk CLL/SLL. In particular, we intend to study the effect of ruxolitinib on disease burden and determine whether treatment with ruxolitinib will delay the time to next treatment of previously untreated patients with high-risk CLL/SLL who are expected to require therapy for CLL/SLL within 4 years according to the above described nomogram (Wierda et al., 2011).

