10.0 CRITERIA FOR REMOVAL FROM THE STUDY

Patients will be removed from the study for the following reasons:

1. Pattern of noncompliance.
2. Toxicity (grade 3 or 4) inducing clinical symptoms necessitating red blood cell or platelet transfusions and not alleviated after dose adjustment.
3. Disease progression that require another therapeutic intervention (an increase in peripheral blood lymphocyte count is expected. If needed anti-CD20 antibody treatment (Rituximab or Ofatumumab) or leukopheresis are allowed).
4. Lack of response (a reduction of 20% of tumor mass or PR) at 6 ± 2 months.
5. Unexpected events (medical or other) that would prevent the patient from staying on study.
6. Patient's or physician's choice. Compliance will be assessed by the P.I. based on the drug accountability documented by the site staff and monitored by the designee. The objective is 100% compliance and the P.I. and his staff will evaluate compliance at each visit, and take appropriate steps to optimize compliance. For the purpose of subgroup analyses, subjects with at least 80% compliance over the total duration of dosing from the first day of dosing to the analysis of the study will be considered to be compliant.

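### Table 8 lets a blood lymphocyte rise of 50% or more count as PD on its own, although the protocol expects lymphocytes to rise; with no PR/PD precedence rule, the CR/PR rate is not uniquely defined

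*Combined protocol and SAP*

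**What the plan says.** **The response rule.** Sections 8.3 and 9.1 assess response at 6 ± 2 months with the IWCLL criteria as set out in Table 8. Blood lymphocytes are a Group A parameter: PR is a fall of at least 50% from baseline, PD a rise of at least 50% over baseline. The footnote then combines the parameters:

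- PR: "at least two of the criteria of group A plus one of the criteria of group B have to be met".
- Stable disease: "SD is absence of progressive disease (PD) and failure to achieve at least a PR".
- PD: "PD: at least one of the above criteria of group A or group B has to be met".

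**The expected lymphocyte rise.** Section 2.1.1, on the earlier CLL symptom trial, reports that in several patients "the number of peripheral blood lymphocyte counts increased and then decreased to or below baseline level", and interprets this as mobilization followed by apoptosis, as with ibrutinib. Section 2.1.2 repeats the finding as part of the rationale: "treatment with ruxolitinib increased and then reduced the number of circulating lymphocytes". Section 10 item 3 lists as a reason for removal "Disease progression that require another therapeutic intervention" and adds in parentheses that "an increase in peripheral blood lymphocyte count is expected".

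**Where the category is used.** Objective 1.1(b) is the rate of CR and PR by these criteria. Section 11 includes CR and PR in the primary endpoint, estimates the response rate with a 95% confidence interval, and counts early drop-outs as non-responders.

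**The concern.** The protocol anticipates a lymphocyte rise as a drug effect, but its response table treats a large enough rise as progression. The allowance in Section 10 is attached to removal from study and is not carried into Table 8, Section 9.1 or Section 11. Table 8 offers no other way out. Its platelet and hemoglobin PD entries require that the change be attributed to the leukemia; its lymphocyte entry has no such qualifier.

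The footnote also fails to make the categories exclusive. Only stable disease is defined by absence of PD, and nothing says which category wins when PR and PD are both met. Two assessors following the protocol could therefore report different CR/PR rates from the same data. In a single-arm trial there is no control group in which a classification error of this kind would show up.

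**Working it through.** The plan states no figure that depends on this rule, so there is none to reproduce. The check is one of logic, followed by simple arithmetic on size.

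**1. One patient, both categories.** Entry requires hemoglobin of at least 12.0 g/dL (Section 3.1.1), and the Group B PR threshold is above 11 g/dL, so a Group B PR criterion is already met at entry. Take a patient with hemoglobin still 12 g/dL, nodes down 60%, spleen down 60% and lymphocytes up 60%.

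- PR: two Group A criteria (nodes, spleen) plus one Group B criterion (hemoglobin). Met.
- PD: one Group A criterion (lymphocytes, 60% being at least 50%). Met.
- Without the lymphocyte trigger: PR only.

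**2. How general the overlap is.** Let nodes, liver, spleen and lymphocytes each be down at least 50%, in between, or up at least 50%. Let marrow meet PR or not (Table 8 has no PD entry for marrow). Assume a Group B PR criterion is met and no Group B PD criterion is. This gives 3 × 3 × 3 × 3 × 2 = 162 patterns.

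| Quantity | Patterns |
|---|---|
| PR and PD both met, as written | 72 |
| Lymphocyte rise is the only PD trigger | 16 |
| of which PR is also met | 11 |
| of which otherwise stable disease | 5 |
| PR and PD both met if an isolated lymphocyte rise is not PD | 72 − 11 = 61 |

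The 16 are the patterns with lymphocytes up and no organ growth: 2 × 2 × 2 × 2, for nodes, liver, spleen and marrow each meeting its PR criterion or not. PR needs at least two of those four: 6 + 4 + 1 = 11. The 61 that remain come from growth at one site alongside two PR criteria elsewhere. A lymphocyte exception alone therefore does not make the categories exclusive. These are counts of logical patterns, not patient frequencies.

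**3. Size per patient.** Section 11 simulates 34 patients at the end of the trial, allowing for 15% drop-out. As drop-outs count as non-responders, the natural denominator is everyone enrolled. Assume 34 / 0.85 = 40, which agrees with the maximum of 40 in Tables 10 and 11. Each patient whose category turns on the rule then moves the CR/PR rate by 1/40 = 2.5 points (1/34 = 2.9 points if only 34 are counted).

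**4. Range.** The documents do not say how many patients would have a rise of at least 50% at assessment. For an assumed 1 to 8 patients who otherwise meet PR, the shift is 1/40 to 8/40, or 2.5 to 20 points.

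**The case against.** **The rise may not matter at assessment.** Section 2.1.1 mentions several patients, gives neither size nor timing, and says counts came back to baseline or below. Some rises may stay under 50% or resolve by 6 ± 2 months. This stands, and is why the size is given per patient with a range. It does not remove the conflict: the window opens at month 4, and nothing in the plan says the rise will have passed by then.

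**The main test is insulated.** This also stands. The paired t-test analyzes change in tumor burden, not response category. The 20% tumor-mass component is assessed by scan and marrow, and the patient in the example may well qualify through it. PD is not itself an analyzed endpoint in Section 11. The exposure is the CR/PR rate.

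**Section 10 already covers it.** Only for removal. It does not say how the response is to be classified.

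**Changing the definition late could favor the drug.** Accrual closed on 06/07/2019 and the trial is single-arm, so this is a fair warning. It argues for fixing the rule before the response analysis and for showing the rate both ways, rather than for replacing one rule by another.

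**Stronger inferences that the documents do not support.** A reader might infer that such patients are scored PD outright, so that downward bias is established. Table 8 makes them PR and PD together; the bias follows only if PD is taken to prevail. A reader might also infer that the trial cannot tell mobilization from progression, and so fails at its central question. Objectives 1.1 and 1.2 are disease burden, CR/PR rate and time to next treatment, and the blood counts, CT and marrow needed to separate the two patterns are all scheduled.

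**Conclusion.** The point holds for response classification. Table 8 conflicts with Sections 2.1.1, 2.1.2 and 10 on what a lymphocyte rise means, and it has no rule for a patient who meets both PR and PD. The CR/PR rate in objective 1.1(b) is therefore not uniquely defined, and it is biased downward by a drug effect if PD is taken to prevail.

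The effect is 2.5 points per affected patient, assuming 40 enrolled. The 2.5 to 20 point range further assumes 1 to 8 affected patients, each otherwise PR. A larger loss should not be read into the protocol, which supplies no proportion with a rise of 50% or more at assessment.

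**What to change.** Reconcile Table 8 with Section 10 item 3 for the purpose of classifying response, before the response analysis:

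1. State in the Table 8 footnote how an isolated lymphocyte rise (at least 50%, no other PD criterion met) is classified.
2. State whether PR or PD prevails when both are met on other parameters. Step 1 alone would leave the 61 overlapping patterns.
3. Report the CR/PR rate with and without patients who meet PR and whose only PD criterion is the lymphocyte rise.

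The cost is a footnote and one extra line in the response table; the data required are already collected under the protocol. There is a small downside: in the version that discounts an isolated rise, true progression seen only in the lymphocyte count is recognized later. Reporting both versions makes that visible. Any consequence for removal from study or for treatment is for the sponsor to reconcile between the two sections and is outside this recommendation.

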9.0 RESPONSE CRITERIA

Response criteria including tumor mass reduction will be assessed at approximately six to eight months by using physical examination, laboratory data, bone marrow analysis (including cytogenetic and, if indicated, molecular analysis), and CT scan analysis.

9.1 Disease Response Criteria

Clinical response will be assessed based on physical examination, CBC, a bone marrow aspiration, a whole body CT scan to be done at screening and 6 ± 2 months in accordance with the IWCLL guidelines (Hallek et al., 2008) as outlined in Table 8. If a 20% reduction in tumor burden is observed at 6 ± 2 months, Treatment will be continued as long as a CR, PR or at least a 20% reduction in tumor mass is achieved and sustained.

10.0 CRITERIA FOR REMOVAL FROM THE STUDY

Patients will be removed from the study for the following reasons:

1. Pattern of noncompliance.
2. Toxicity (grade 3 or 4) inducing clinical symptoms necessitating red blood cell or platelet transfusions and not alleviated after dose adjustment.
3. Disease progression that require another therapeutic intervention (an increase in peripheral blood lymphocyte count is expected. If needed anti-CD20 antibody treatment (Rituximab or Ofatumumab) or leukopheresis are allowed).
4. Lack of response (a reduction of 20% of tumor mass or PR) at 6 ± 2 months.
5. Unexpected events (medical or other) that would prevent the patient from staying on study.
6. Patient's or physician's choice. Compliance will be assessed by the P.I. based on the drug accountability documented by the site staff and monitored by the designee. The objective is 100% compliance and the P.I. and his staff will evaluate compliance at each visit, and take appropriate steps to optimize compliance. For the purpose of subgroup analyses, subjects with at least 80% compliance over the total duration of dosing from the first day of dosing to the analysis of the study will be considered to be compliant.

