3.1.1 Inclusion criteria

- 1) Subjects who are able to understand and sign an informed consent document.
- 2) Subjects 18 years of age or older.
- 3) Subjects must be diagnosed with CLL/SLL and do not meet the IWCLL criteria for treatment (Hallek et al., 2008).
- 4) Patients should be previously untreated or have only been treated with single agent ibrutinib therapy for a period of < 3 months and were deemed ibrutinib intolerant.
- 5) Patients whose expected time to CLL/SLL treatment, according to our nomogram (Figure 1), is four years of less.
- 6) Subjects with hemoglobin values at the screening visit equal to or greater than 12.0 g/dL.
- 7) Subjects with a platelet count of at least $100 \times 10^9/L$ at the screening visit.
- 8) Subjects with an absolute neutrophil count (ANC) of equal to or higher than $0.5 \times 10^9/L$ at the screening visit.

- 9) Subject who are willing to undergo a bone marrow aspiration and biopsy and CT scan for disease burden assessment.
- 10) Patient who are capable to return to MDACC for follow-up.
- 11) Subjects with an Eastern Cooperative Oncology Group (ECOG) performance status of 0, 1 or 2.
- 12) Patient must be capable of swallowing the Ruxolotinib capsules (tablets).

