8.1 Outside Physician Participation during Treatment

1. MDACC Physician communication with the outside physician is required prior to the patient returning to the local physician. This will be documented in the patient record
2. A letter to the local physician outlining the patient's participation in a clinical trial will request local physician agreement to supervise the patient's care (Appendix H)
3. Protocol required evaluations outside MDACC will be documented by telephone, fax or e-mail. Fax and/or e-mail will be dated and signed by the MDACC physician, indicating that they have reviewed it.
4. Changes in drug dose and/or schedule must be discussed with and approved by the MDACC physician investigator, or their representative prior to initiation, and will be documented in the patient record.

5. A copy of the informed consent, protocol abstract, treatment schema and evaluation during treatment will be provided to the local physician.
6. Documentation to be provided by the local physician will include drug administration records, progress notes, reports of protocol required laboratory and diagnostic studies and documentation of any hospitalizations.
7. The home physician will be requested to report to the MDACC physician investigator all life threatening events within 24 hours of documented occurrence.
8. Patient will have a physical exam every 1-2 months.

Patients are allowed to have hematology and biochemistry tests performed in outside laboratory facilities. Laboratory results will be obtained by the research staff assigned to this study. The PI or treating physician listed on the delegation of authority log will review outside labs and determined the clinical significance of these labs. The physician will sign and date the outside lab result.

Follow-ups and disease burden assessments will only be performed by the MD Anderson Cancer Center team. Patients must be followed for SAE/AEs until at least 30 days after the last dose of study drug. SAE/AE will be assessed on their next visit to the leukemia clinic at MDACC. Participant will be removed from the protocol study after the 30-day post-treatment visit/assessment.

All protocol specific data will be entered into PDMS/CORe.

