11.0 STATISTICAL CONSIDERATIONS

The study will be conducted at MDACC only. The primary endpoint will assess the clinical response (CR, PR, and a 20% reduction in tumor mass as assessed by a body scan and bone marrow aspiration/biopsy) at 6 ± 2 months after initiation of therapy.

We will incorporate an informal futility analysis when half of the total patients have reached 6 ± 2 months after initiation to assess whether the average change in the tumor mass score is less than zero (calculated as the score at enrollment minus the score at six months). If the average at this time is less than zero, the trial will be stopped early.

Because no treatment is the standard of care for these patients, we will routinely analyze the outcome of our Ruxolitinib-treated patients at a 6 \pm 2 month interval and compare their clinical outcome to that of patient who elected to receive no treatment.

Table 9 shows the probability of stopping early under several different scenarios, as well as how the overall power is for the primary analysis is affected by early stopping. The operating characteristics were produced in R version 2.13.0 by simulating 5000 trials with 17 patients at the interim and 34 patients at the end of the trial, accounting for a 15% drop out rate. The simulations stop early if the average change at 6 months is less than zero, and formally tests whether the change is not equal to zero at the final analysis using a paired *t*-test.

Table 9. Operating characteristics

True tumor burden difference (baseline score minus score at 6 months)	True SD of the Difference	Prob(Stop Early)	Power for Final Analysis
-1	2	0.9818	0.0026
0	2	0.5068	0.0218
1	2	0.0202	0.8064
2	2	0.0000	0.9998
-1	4	0.8398	0.0014
0	4	0.4958	0.0274
1	4	0.1584	0.2876
2	4	0.0198	0.8074

For primary analysis, the paired *t* test will be used to evaluate the changes of tumor burden from baseline to 6 \pm 2 months after initiation of therapy. Response rate will be estimated with 95% confidence interval. Patients who drop out early will be counted as non-responders. The Kaplan-Meier method will be used to estimate time to next treatment, and will compared to our historical data (Wierda et al., 2011) using Cox proportional hazards model, adjusting for effects of covariates. If necessary and applicable, appropriate methods such as propensity score matching will be used to match the patients of this study with the historical data to reduce comparison bias.

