12.0 REPORTING REQUIREMENTS

Adverse events will be reported in accordance with the Leukemia-specific Adverse Event Recording and Reporting Guidelines (Appendix G). Adverse events will only be collected up to 30 days after the last dose of ruxolitinib. Adverse event reporting will be as per the NCI version 4 criteria and the MDACC Leukemia Specific Adverse Event Recording and Reporting Guidelines.

Adverse events will be recorded on the Adverse Event Record (AER) for each patient after every protocol visit. The Principal Investigator will sign and date the Adverse Event record for every patient after every protocol visit. Following signature, the Adverse Event Record will be used as source documentation for the adverse events for attribution.

Concomitant medications will be captured in the electronic medical record and not needed in the data capture.

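### Section 11 has no rule for patients given the anti-CD20 antibody or leukapheresis that Section 10 allows, so tumour reduction from an antibody could be credited to ruxolitinib

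*Combined protocol and SAP*

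**What the plan says.** Section 10.0 item 3 removes patients whose progression needs another intervention. Its parenthesis adds that a lymphocyte rise is expected and continues: "If needed anti-CD20 antibody treatment (Rituximab or Ofatumumab) or leukopheresis are allowed".

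Section 11.0 places the primary endpoint (CR, PR or a 20% tumour reduction on scan and marrow) at 6 ± 2 months and tests the change in tumour burden with a paired t-test. Its only rule for events after baseline is "Patients who drop out early will be counted as non-responders". The same change scores drive the futility look at half the patients: "If the average at this time is less than zero, the trial will be stopped early". There is no randomised control. The plan will "compare their clinical outcome to that of patient who elected to receive no treatment".

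For the secondary objective, "The Kaplan-Meier method will be used to estimate time to next treatment", with a comparison to historical data. The plan does not say whether the allowed co-treatment is an event.

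On data, Section 12.0 states: "Concomitant medications will be captured in the electronic medical record and not needed in the data capture".

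**The concern.** Two readings of item 3 lead to two different results for the same patient. If the patient is treated as removed, the drop-out rule plausibly makes that patient a non-responder, although Section 11.0 does not equate removal with dropping out. If the patient stays on study, no rule applies, and the scan, marrow and tumour score are used as they stand.

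On the second reading, a within-patient comparison cannot separate an antibody effect from a ruxolitinib effect, and patients who elected no treatment do not help to separate them. The response rate and the mean change could rise for a reason other than the study drug. Because the interim look uses the same scores, an ineffective drug would also be less likely to be stopped. If co-treatment is not an event, time to next treatment would look longer against the historical data.

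Anti-CD20 antibody is the main issue, because the endpoint is read on scan and marrow. Leukapheresis bears mainly on the blood-lymphocyte row of Table 8.

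**Working it through.** **Inputs from Section 11.0.** 17 patients at the interim look and 34 at the end, after allowing for 15% drop-out. The trial stops if the interim mean change is below zero. The final paired t-test is against a change not equal to zero. Alpha is not stated, so 0.05 two-sided is assumed.

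**Inputs that are assumptions.** The number of co-treated patients k (1 or 3), the added tumour reduction s per co-treated patient (2, 4 or 6 units), random placement of these patients, and no ruxolitinib effect. The documents give no co-treatment rate, no effect size and no scale for the tumour score.

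**Step 1: reproduce Table 9.** Simulated normal differences, with a stop if the mean of the first 17 is below 0, then t = mean / (SD/√34) on 34.

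- True difference 1, SD 2: power about 0.81 and early stop 0.019 (Table 9: 0.8064 and 0.0202).
- True difference 0: rejection rate about 0.025 at SD 2 and at SD 4 (Table 9: 0.0218 and 0.0274).

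All eight rows agree within 2 points. Without the interim look, the rejection rate at zero difference is about 0.05. With the futility stop, about 0.025 is the planned figure.

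**Step 2: add co-treatment, no drug effect.** Each co-treated patient's change is raised by s, so the expected mean rises by k × s / 34. For example, 1 × 4 / 34 = 0.12 units and 3 × 6 / 34 = 0.53 units. The chance of a significant benefit, which is 0.025 with no co-treatment, becomes:

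| k | SD | s = 2 | s = 4 | s = 6 |
|---|---|---|---|---|
| 1 | 2 | 0.034 | 0.041 | 0.045 |
| 3 | 2 | 0.063 | 0.105 | 0.141 |
| 1 | 4 | 0.030 | 0.034 | 0.039 |
| 3 | 4 | 0.042 | 0.062 | 0.084 |

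These are for the final test on 34. Including the interim look changes them by about 0.001.

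**Step 3: futility rule, SD 2, no drug effect.** The chance of stopping falls from 0.50 to 0.45-0.37 with one co-treated patient and to 0.36-0.18 with three.

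**Step 4: response rate.** 34 / (1 − 0.15) = 40 patients, which matches the maximum in Tables 10 and 11. Each patient whose status changes moves the rate by 1/40 = 2.5 points. From an assumed 8/40 = 20% (exact 95% CI 9.1-35.6%), one gives 9/40 = 22.5% (10.8-38.5%) and three give 11/40 = 27.5% (14.6-43.9%).

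**Step 5: the proposed sensitivity analysis.** A fixed amount is subtracted from each co-treated patient's change. When the amount equals the true shift, the chance of a false benefit returns to 0.025. When there is no co-treatment effect and ruxolitinib has a real 1-unit effect (SD 2), subtracting 4 units lowers the chance of a significant result from 0.81 to 0.66 with one co-treated patient and to 0.34 with three.

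**The case against.** The strongest objection is that crediting depends on three conditions: the patient stays on study, the antibody is given before the assessment, and the score is used as observed. The allowance sits inside a removal criterion, so a co-treated patient might simply leave and fall under the drop-out rule. This stands as a limit on the claim. A reader might infer that the plan will credit antibody responses to ruxolitinib. The text supports only that it could.

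The size is also wholly assumed. A shift of 6 units at SD 2 is 3 SD per patient, while the largest difference in Table 9 is 2 units. At a 2-unit shift the false-benefit figures are 0.034 and 0.063. Co-treatment may be rare, because of the entry criterion "Subjects must be diagnosed with CLL/SLL and do not meet the IWCLL criteria for treatment". This stands too.

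A reader might further infer that co-treated patients could not be traced. The documents do not support that. Section 8.1 says "Documentation to be provided by the local physician will include drug administration records, progress notes", and both it and Section 11.2 send protocol-specific data to the study database. Dates of CLL treatment arguably belong there, since time to next treatment is a secondary objective. What remains is narrower: Section 12.0 does not require concomitant medication in the data capture, so the analysis data need not show who was co-treated.

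None of this supplies the missing rule. The prohibited-medication criterion in Section 3.1.2 does not name anti-CD20 antibody, and the drop-out sentence does not reach a patient who remains on study.

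**Conclusion.** The gap is real and should be fixed, with medium confidence. Under the most natural reading of Section 10.0 item 3, a patient given anti-CD20 antibody before the 6 ± 2 month assessment is scored as observed in an uncontrolled before-and-after analysis, and the resulting reduction could count as a ruxolitinib effect.

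The size rests on assumed numbers of co-treated patients and assumed shifts. With one such patient the effect is small: a false-benefit chance of at most about 0.045 against 0.025, and 2.5 points on the response rate. With three it is no longer negligible: up to about 0.14 at SD 2, and 7.5 points if all three change status (3 × 2.5).

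Table 9 itself is sound for the design that it simulates. That simulation has no term for co-treatment.

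**What to change.** 1. Reconcile Sections 10.0 and 11.0 on whether a patient given the allowed co-treatment stays on study.
2. State in Section 11.0 that patients given anti-CD20 antibody or other CLL-directed treatment before the 6 ± 2 month assessment count as non-responders in the response rate, in line with the existing drop-out rule. Say in the same place whether leukapheresis is included.
3. Keep the paired t-test and the futility mean as observed. Beside the t-test, pre-specify one sensitivity analysis that subtracts an amount, in steps from zero, from each co-treated patient's change and reports where a significant benefit is lost. It drives no decision.
4. Count the first anti-CD20 or other CLL-directed drug treatment as a time-to-next-treatment event, or report that analysis both ways.
5. Record the type and date of co-treatment in the case report form.

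The cost is a few sentences and two case report form fields. The response rate may be slightly lower, by 2.5 points for each co-treated patient who would otherwise have been scored a responder. The t-test and futility rule keep their planned properties. The sensitivity analysis shows a co-treatment effect but does not remove it, and it is pessimistic when too much is subtracted, so it should not replace the main result. What patients may receive is unchanged.
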